4.3. Exploratory objectives

- To assess parasite genomic and transcriptomic variation at baseline and at select post-treatment timepoints.
- To assess human genomic variation (i.e., HBB type) and association with parasite measures.
- To assess the association of parasite and plasma biomarkers on malaria transmission efficiency.
- To assess the efficiency of *Plasmodium* transmission to mosquitoes before and after enrichment of gametocytes by MACS.
- To determine the association between gametocyte density and mosquito infection rates, before and after MACS enrichment, to estimate possible loss in per-gametocyte infectivity following treatment.

5. STUDY DESIGN

This is a five arm, single-blinded, randomized clinical trial. The study will be conducted according to the following steps for each individual:

Individuals aged 10-50 years will be invited to participate. They will be asked to provide informed consent and assent (for those under 18 years of age). After obtaining the informed consent and assent (if applicable), participants will undergo a screening including clinical evaluation and for the presence of microscopically detectable *P. falciparum* infection. Individuals with ≥ 16 gametocytes/ μL will be recruited and go through additional screening including haemoglobin measurement, CBC, assessment of renal and liver functions, and pregnancy tests. Recruitment will continue until 100 infected individuals with microscopically detectable *P. falciparum* gametocytes ($\geq 16/\mu\text{L}$) are recruited and randomised.

Individuals who meet the inclusion and exclusion criteria will be randomised in a 1:1:1:1:1 ratio into five groups (arms); ASAQ, ASAQ-PQ (0.25mg/kg), AL, ALAQ, ALAQ-PQ (**Table 1**). Randomisation will be performed by the study pharmacist. All other staff will be blinded to the treatment allocation.

Table 1. Treatment arms

Arm	ACT	PQ (mg/kg)	Sample size
1	ASAQ		20
2	ASAQ	0.25	20
3	AL		20
4	ALAQ		20
5	ALAQ	0.25	20

Each participant will be followed for 28 days. Participants will receive a full clinical and parasitological examination on days 2, 7, 14, 21, 28 after receiving the first dose of the study drugs. Blood samples will be taken at all visits for parasitology (microscopy, and whole blood for qRT-PCR) and serology with additional samples for haematology and biochemistry analysis at days 0, 2 and 14. A clinical and haematological examination will also be performed on day 1, at which point no other samples will be collected.

Infectivity to locally reared mosquitoes will be assessed with membrane feeding assays at baseline, on the final day of treatment (day 2) and at days 7 and 14 for all participants. Feeds will then be performed at day 21 for any individuals infectious at day 7 or 14; and at day 28 for any individuals infectious at day 14 or 21. Magnetic-activated cell sorting (MACS) to enrich for gametocytes will be done at two timepoints per individual, followed by MFA.

In addition to this passive monitoring, participants will be prompted to contact the study coordinators if they feel sick at any point during follow up. A full clinical examination will be performed, and treatment will be provided according to national treatment guidelines.

5.1. Study site

The Malaria Research and Training Centre (MRTC) in Bamako, Mali will use the field site of Ouelessebougou for recruitment. The MRTC has the unique position of being one of very few sites in Africa that can study malaria transmission endpoints. Since 2013 the MRTC successfully carried out similar trials at this site with great success, in collaboration with the University of California San Francisco, the London School of Hygiene and Tropical Medicine and the Radboud University Medical Center, Nijmegen, the Netherlands. In the 2013-2014 study, the MRTC demonstrated the efficacy of SLD PQ of doses of 0.125mg/kg or greater in combination with dihydroartemisinin-piperaquine for blocking *P. falciparum* transmission safely in G6PD normal Malian males from the age of 10-50 years [8]. MRTC has already established all the assays required for the study described in this protocol.

The MRTC is experienced in conducting Good Clinical Practice (GCP) compliant clinical trials including phase 1, 2, 3 and 4 of malaria vaccine and drug studies. Ouelessebougou village has been conducting ongoing clinical research since 2008 and is endemic for malaria with marked seasonality and a high burden of malaria in both children and adult populations. In recent years the prevalence of *P. falciparum* malaria in children under 5 years of age has ranged between 14% and 54% during the transmission season. The frequency of G6PD deficiency is in the range of 10 to 15%.

5.2. Study population

The study population will be derived from individuals aged 10-50 years with asymptomatic *P. falciparum* malaria infection who agree to be screened for malaria infection.

For the randomised trial, we will aim to recruit 100 individuals. Eligible individuals will have microscopically detectable *P. falciparum* gametocyte densities of ≥ 16 gametocytes/ μL .

5.3. Intervention

Individuals who meet the inclusion criteria in the current study will be randomised in a 1:1:1:1:1 ratio into five groups (arms); ASAQ, ASAQ-PQ (0.25 mg/kg), AL, ALAQ, ALAQ-PQ (0.25 mg/kg). Randomisation will be performed by the study pharmacist. All staff other than the study pharmacist and clinician will be blinded to the treatment allocation. Participants will be told prior to enrolment that they can ask at any time which treatment arm they are in. The clinician or pharmacist will discuss this with them.

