8.4. Blinding

This is a single-blind randomised controlled trial. The treating physician and staff involved with assessing all laboratory outcomes of the study are blinded, but no placebo will be used. The study pharmacist will be unblinded and responsible for randomisation and treatment administration. Entomology staff involved in the mosquito feeding assays will be blinded for the parasitology results.

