9.2. Adverse Event Data Collection

Safety assessments will be performed and recorded by the trial clinicians. All AEs/reactions, observed by the trial clinicians or by the subject, will be accurately documented in the case report form. For each event/reaction the following details will be recorded:

1. Description of the event(s)/reaction(s)
2. Date and time of occurrence
3. Duration
4. Intensity
5. Relationship with the intervention
6. Action taken, including treatment

7. Outcome

In addition, symptoms will be ranked as (1) mild, (2) moderate, or (3) severe, depending on their intensity. All AEs except fever will be judged for their intensity according to the following scale:

- Mild (grade 1): awareness of symptoms that are easily tolerated and do not interfere with usual daily activity
- Moderate (grade 2): discomfort that interferes with or limits usual daily activity
- Severe (grade 3): disabling, with subsequent inability to perform usual daily activity, resulting in absence or required bed rest

For fever, the following scale will be used:

- Mild (grade 1): 37.5 - 38.0°C
- Moderate (grade 2): > 38.0 to 39.0°C
- Severe (grade 3): > 39.0°C

When an AE/SAE occurs, it is the responsibility of the principal investigators and trial clinicians to review all documentation (e.g., hospital progress notes, laboratory, and diagnostics reports) related to the event. The principal investigators and trial clinicians will then record all relevant information regarding an AE/SAE on the Case Report Form (CRF) or SAE Report Form, respectively. Furthermore, the trial clinicians will attempt to establish a diagnosis of the event based on signs, symptoms, and/or other clinical information. In such cases, the diagnosis should be documented as the AE/SAE and not the individual signs/symptoms.

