9.4. Assessment of causality

The principal investigators and trial clinicians are obligated to assess the relationship between study procedures and the occurrence of each AE/SAE. The clinicians will use clinical judgment to determine the relationship. Alternative causes, such as natural history of the underlying diseases, concomitant therapy, other risk factors and the temporal relationship of the event to the study procedures will be considered and investigated. The relationship of the AE with the study procedures will be assessed considering the factors listed under the following categories:

Table 7. Causality

Definitely Related	
• reasonable temporal relationship• follows a known response pattern• clear evidence to suggest a causal relationship• there is no alternative aetiology
---------------------------	---

Probably Related	
 • reasonable temporal relationship • follows a suspected response pattern (based on similar agents) • no evidence of a more likely alternative aetiology
Possibly Related	
 • reasonable temporal relationship • little evidence for a more likely alternative aetiology
Unlikely Related	
 • does not have a reasonable temporal relationship 
OR
 
 • good evidence for a more likely alternative aetiology
Not Related	
 • does not have a temporal relationship 
OR
 
 • definitely due to an alternative aetiology

Note: Other factors will also be considered for each causality category when appropriate. Causality assessment is based on available information at the time of the assessment of the AE. The investigator may revise the causality assessment as additional information becomes available.

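### Section 5.3 exempts the clinician from blinding, while Sections 5 and 8.4 leave only the pharmacist unblinded, so it is unclear whether adverse events are judged blind to arm

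*Protocol*

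**What the plan says.** Three sections of the Protocol state who knows the allocation.

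- **Section 5 (Study design)** gives randomisation to the study pharmacist and continues: "All other staff will be blinded to the treatment allocation".
- **Section 5.3 (Intervention)** exempts two roles: "All staff other than the study pharmacist and clinician will be blinded to the treatment allocation". It adds: "Participants will be told prior to enrolment that they can ask at any time which treatment arm they are in". On who answers such a request, it says: "The clinician or pharmacist will discuss this with them".
- **Section 8.4 (Blinding)** says: "The treating physician and staff involved with assessing all laboratory outcomes of the study are blinded, but no placebo will be used". The only role it describes as unblinded is the pharmacist, who randomises and gives the treatment.

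Other sections say who makes the safety judgements.

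- **Section 9.2:** "Safety assessments will be performed and recorded by the trial clinicians". Apart from fever, intensity is graded by how far symptoms limit daily activity.
- **Section 9.4** makes the principal investigators and trial clinicians responsible for causality: "The clinicians will use clinical judgment to determine the relationship".
- **Section 8.2** leaves withdrawal after an adverse event to the study clinician's discretion.
- **Section 7.2** lists the frequency and prevalence of adverse events, including treatment-related ones, as a secondary outcome.

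**The concern.** The trial is single-blind, uses no placebo and lets participants learn their arm. Staff blinding is therefore the only blinding it has. For laboratory outcomes it is stated consistently. For the clinician it is not, and clinicians produce the safety data that depend on judgement.

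The Protocol itself gives an unblinded assessor reasons to expect differences between arms. Section 12.2.2 describes haemolysis with primaquine, and Section 12.2.5 reports more mild, mainly gastrointestinal, events with the triple combination than with artemether-lumefantrine alone. Someone who knows the arm could grade or attribute an ambiguous symptom differently, or decide differently on withdrawal. The contrasts at stake are the matched ones: ASAQ against ASAQ-PQ, AL against ALAQ, and ALAQ against ALAQ-PQ. Analysis cannot restore blinding once events have been graded with knowledge of the arm, so the rule has to be settled as a matter of conduct.

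**Working it through.** The Protocol states no figure on this point, so the check is a comparison of its sections.

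**Step 1. Status of each role.**

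| Role | Section 5 | Section 5.3 | Section 8.4 |
|---|---|---|---|
| Study pharmacist | exempt (by implication) | unblinded | unblinded |
| Clinician or treating physician | blinded (by implication; not named) | unblinded | blinded (named) |
| Laboratory assessors | blinded (by implication) | blinded (by implication) | blinded (named) |

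The pharmacist and laboratory rows agree across the three sections. The clinician row does not. Only Section 8.4 blinds the physician by role; Section 5 does so through a general statement about all other staff.

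**Step 2. Is 5.3 a slip of wording?** The section goes on to give the clinician a part in telling participants their arm, which requires access to the allocation. Its two statements support each other, so the conflict cannot be dismissed as a stray word.

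**Step 3. Is the unblinded clinician the adverse event assessor?** The Protocol uses four terms: clinician (5.3), treating physician (8.4), trial clinicians (9.2 and 9.4) and study clinician (8.2). It never says whether these are the same people. It describes no separate blinded safety assessor. That they overlap is a reasonable inference, not a stated fact.

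**Step 4. Which outcomes are exposed?**

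- *Exposed if 5.3 is followed:* adverse event intensity, causality and hence treatment-related adverse events, and discretionary withdrawal. In Section 7.2 this is part of one of 14 secondary outcomes.
- *Little affected:* the primary outcome, change in mosquito infection rate at day 2 (7.1), because all three sections blind the staff who assess it; measured haemoglobin (10.6); and the severe haematological event, defined as a fall in haemoglobin of more than 40% (9.3).

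**Step 5. Can the effect be sized?** Not from the documents. As a scale only, take 20 participants per arm (Table 1) and the p < 0.05 threshold (11.1). If x participants in one arm have a related event and none in the other do, the two-sided Fisher p-value is 2 × C(20, x) / C(40, x):

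- x = 2: 2 × 190 / 780 = 0.49
- x = 3: 2 × 1,140 / 9,880 = 0.23
- x = 4: 2 × 4,845 / 91,390 = 0.11
- x = 5: 2 × 15,504 / 658,008 = 0.047

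The counts are assumed. Three participants, or 15 percentage points of one arm, would not by themselves produce a significant difference from a comparator with none. A shift of three added to a true 2 against 0 would move p from 0.49 to 0.047. Nothing in the Protocol says how large a shift to expect.

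**The case against.** **Limited reach.** The primary outcome is assessed by blinded staff, and Section 9 names haemolysis as the major safety endpoint, which is followed by measured haemoglobin. No primary conclusion would change. This stands, and it keeps the point below the level of a critical flaw.

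**Section 5.3 may be intended.** It gives the clinician a deliberate part in discussing allocation, so the error could lie in Sections 5 and 8.4. The documents do not settle this. The remedy must therefore allow for either intention, although two of the three sections favour a blinded clinician.

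**Blinding the clinician would be incomplete.** There is no placebo, the regimens differ, and participants can learn their arm and mention it. This also stands. A blinded clinician reduces the risk but does not remove it.

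A reader might also infer three stronger points that the documents do not support:

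- *That the DSMB pause rule depends on the clinician's attribution of adverse events.* Under Section 9.6 the pause follows a serious event or SUSAR that the DSMB itself deems related. Adverse event data reach the DSMB in monthly reports, but their frequency does not trigger the pause.
- *That the bias would match any real difference the trial could show.* No shift is documented, and 3 of 20 against 0 of 20 gives p = 0.23.
- *That the unblinded clinician is stated to be the person who grades events.* This is inferred from overlapping role names.

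**Conclusion.** The contradiction is real, and nothing in the Protocol resolves it. If Section 5.3 is the rule in use, and if its clinician is among the trial clinicians who assess safety, then the intensity grading, causality and discretionary withdrawal behind the treatment-related adverse event comparison could be decided with knowledge of the arm. The second condition is likely but not stated.

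The size of any bias is unknown and cannot be derived from the documents. The exposure is confined to the judged safety items; the primary outcome and the measured haemoglobin endpoints are little affected. This is an internal inconsistency that should be fixed before adverse events are graded. It is not a threat to the primary result.

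**What to change.** Reconcile Sections 5, 5.3 and 8.4 and use one term for each role.

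- **Preferred route:** bring 5.3 into line with 5 and 8.4. Remove the clinician from the exemption. State that the clinicians who grade adverse events, judge causality and decide on withdrawal are blinded. Make the pharmacist the person who discloses allocation on request, and log each disclosure with its date.
- **Alternative, if the sponsor intends an unblinded clinician:** correct Sections 5 and 8.4 to say so, and report treatment-related adverse events as an unblinded assessment.

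The cost is a few sentences and a short log. The pharmacist already holds the codes (8.3), gives the treatment (8.4) and is one of the two roles allowed to discuss allocation (5.3). Some unblinding will remain because there is no placebo and participants may reveal their arm. The Protocol should acknowledge this.

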5.4. Sample size calculation

For sample size considerations, we estimated the infectivity for participants in previous trials in the same study setting [3], [4], [8], [23] using a mixed effects logistic regression model that accounted for correlation between mosquito observations from the same participant. Based on a mixed effects logistic regression we looked at 100 simulations with an expected reduction in infectivity of 90%, an expected baseline proportion of infectivity of 17% for the average participant, and an expected intra-cluster correlation of 0.5. We estimated 88% empirical power to detect $>80\%$ reduction in infectivity with a one-tailed test with a 0.025 level of significance when including 20 participants and dissecting 50 mosquitos per participant at each timepoint.

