7. OUTCOME MEASURES

7.1. Primary outcome measure

Median within person percent change (presented as percent reduction) in mosquito infection rate in infectious individuals from baseline (day 0, pre-treatment) to day 2 post treatment in the ASAQ, ASAQ-PQ, AL, ALAQ and ALAQ-PQ arms.

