11.1. Analysis plan

Mosquito infectivity will be assessed at three levels: the mean number of oocysts in a sample of mosquitoes (i.e. oocyst intensity), the proportion of mosquitoes infected with any number of oocysts (i.e. mosquito infection rate), and the infectivity of the study participant to any number of mosquitoes (i.e. infectivity to mosquitoes). The primary outcome measure will be the percent change in mosquito infection rate within each arm by day 2 compared to baseline, with other time-points of infectivity assessments as secondary outcomes. Percent change will be reported as percent reduction (with 100% as total reduction of transmission, and negative values as enhanced transmission). Other secondary transmission outcomes are as described in the 'Objectives' section above. Some exploratory objectives may be published separately from the main primary/secondary outcomes.

Statistical analysis will be conducted using the most recent STATA and SAS versions (16.0 and SAS version 9.4 at time of writing). Mosquito infection data will be analysed at time-points after baseline only for those individuals who are infectious at baseline, although the data and analyses from all enrolled individuals will be published in the appendix for completeness. Individuals will be classified as infectious to mosquitoes if they infect at least 1 mosquito, with any number of oocysts. Infectivity to mosquitoes and parasite/gametocyte prevalence will be compared within and between treatment arms using generalised linear models (family: binomial, z-score, co-efficient with 95% CI) or fishers exact tests. Absolute haemoglobin density and percent change in haemoglobin density (relative to baseline) will be compared using paired t-tests (t-score for difference compared to day 0) and two-way t-tests (t-score for difference between ACT matched treatment groups at each time-point). The proportion of gametocytes that are male will be calculated for all values with total gametocyte densities of 0.2/ μ L and over. Gametocyte circulation time will be calculated to determine the average period (in days) that a mature gametocyte circulates in the blood prior to clearance, using a deterministic compartmental model that assumes a constant rate of clearance and has a

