random effect to account for repeated measures on individuals, as described previously [29]; circulation time will be analysed using t-tests (t score for difference between ACT matched treatment groups) or linear regression analyses. Area under the curve (AUC) of gametocyte density per participant over time will be calculated using the linear trapezoid method [30] using the first 28 days of observation only, and analysed by fitting linear regression models to the log10 adjusted AUC values, with and without adjustment for baseline gametocyte density (t-score, coefficient with 95% CI). All other analyses of quantitative data will be performed using Wilcoxon sign rank tests (z-score for difference compared to matched values at day 0) and Wilcoxon rank-sum tests (z-score for difference between ACT matched treatment arms at each time-point). The nonparametric van Elteren's test, an extension of the Wilcoxon rank sum test, will be used to compare the infectivity between treatment arms after adjusting for gametocyte density, as previously described [19]. This will compare infectivity between groups after stratifying into categories based on total gametocytes per microliter. Within these bins differences in infectivity between arms will be tested, thereby investigating sterilizing effects of gametocytocidal drugs. For all analyses, the threshold for statistical significance will be set at $p < 0.05$.

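### The 88% power in Section 5.4 is for a mixed-model test of a reduction above 80%, but Section 11.1 gives the primary outcome a Wilcoxon test of no change.

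*Protocol*

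**What the plan says.** **Section 5.4 (sample size).** The method is given as "Based on a mixed effects logistic regression we looked at 100 simulations". The inputs are "an expected reduction in infectivity of 90" percent, a 17% baseline proportion for the average participant, an intra-cluster correlation of 0.5, 20 participants and 50 dissected mosquitoes per participant and timepoint. The result is stated as "We estimated 88% empirical power to detect" a reduction above 80%, one-tailed at 0.025.

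**Section 7.1 (primary outcome).** "Median within person percent change (presented as percent reduction) in mosquito infection rate in infectious individuals from baseline" to day 2, for each of the five arms.

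**Section 11.1 (analysis plan).** Three statements bear on the primary outcome:
- "Mosquito infection data will be analysed at time-points after baseline only for those individuals who are infectious at baseline", with results for everyone enrolled going to an appendix.
- Binomial generalised linear models (or Fisher's exact test) are assigned to binary infectivity and to parasite and gametocyte prevalence. Mosquito infection rate is not in that list.
- "All other analyses of quantitative data will be performed using Wilcoxon sign rank tests (z-score for difference compared to matched values at day 0"), with significance at p < 0.05 throughout.

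The 80% threshold, the one-tailed test and the mixed-effects logistic model appear nowhere outside 5.4.

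**The concern.** A power figure describes one test of one null hypothesis. Section 5.4 asks whether the reduction in an arm exceeds 80%. The only within-arm test that 11.1 offers for the primary outcome asks whether there was any change from day 0.

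The second question is much easier to answer yes. An arm that halves infectivity and an arm that nearly abolishes it would both be reported as significant, so the primary p-value cannot tell them apart. The sole justification for 20 per arm would then rest on a hypothesis that this protocol does not test.

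**Working it through.** **1. The two sections side by side**

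| | Section 5.4 | Sections 7.1 and 11.1 |
|---|---|---|
| Summary | Reduction estimated by mixed-effects logistic model | Median within-person percent change |
| Null | Reduction is at most 80% | No change from day 0 |
| Participants | 20 | Those infectious at baseline |

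**2. Inputs.** From 5.4: average participant 17%, so logit(0.17) = ln(0.17/0.83) = -1.59; ICC 0.5; 20 participants; 50 mosquitoes per timepoint. The protocol does not give the scale of the ICC. I read it on the latent logit scale: ICC = σ²/(σ² + π²/3) = 0.5, so σ² = π²/3 = 3.29.

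Model: u_i ~ N(0, 3.29); p_i0 = expit(-1.59 + u_i); infected counts are binomial with 50 mosquitoes on day 0 and on day 2. A true reduction r can be read in three ways:
- a common logit shift that moves the average participant from 17% to 17% × (1 - r), which is 1.7% at r = 0.90;
- a common odds ratio of 1 - r;
- each person's rate multiplied by 1 - r.

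**3. The plan's own figure.** I fitted a random-intercept logistic model by maximum likelihood and used a one-sided Wald test against 80% at z = 1.96, with 250 to 700 trials per variant.
- Literal reading, common logit shift: 96%.
- Odds-ratio reading: 96%, or 85% if the test is then made on the risk ratio.
- 17% taken as the marginal mean: 82% to 85%, or 74% for an odds-ratio effect tested on the risk ratio.
- Random-effect variance of 0.5 in place of ICC 0.5: 91% to 92%.

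The readings run from 74% to 96% and span 88%. The exact (Clopper-Pearson) 95% interval for 88 of 100 simulations is 80.0% to 93.6%. On the literal reading, the test rejects in 2.4% of trials at a true 80% reduction, as it should. Against a null of zero, the same model has 100% power at a true 90% reduction in every variant, so the 88% can only belong to the 80% null.

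**4. Size of the analysed set.** The expected number with at least one infected mosquito at baseline is 20 × E[1 - (1 - p_i0)^50] = about 18.2 (16.5 if 17% is the marginal mean).

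**5. The test that 11.1 assigns.** Two-sided Wilcoxon signed-rank, day 2 against day 0, baseline-infectious participants only, 2,000 trials per cell. Percentage of trials with p < 0.05:

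| True reduction | Logit shift | Odds ratio | Each rate × (1 - r) |
|---|---|---|---|
| 30% | 86% | 76% | 96% |
| 50% | over 99% | over 99% | 100% |
| 80% | 100% | 100% | 100% |
| 90% | 100% | 100% | 100% |

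The test cannot distinguish 50%, 80% and 90%.

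**The case against.** **The assignment is inferred, and an SAP may exist.** Section 11.1 does not name the test for the primary outcome; Wilcoxon reaches it through the residual clause. The primary objective in 4.1 is to assess the within-person reduction, not to prove that it exceeds 80%, and an SAP could add a comparison with 80%. This stands as a limit on wording: the supportable statement is that the benchmark is not tested in this protocol, not that it will never be tested. It does not remove the point, because the protocol fixes a test with a different null.

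**Stronger readings that the document does not support**
- *The 88% is wrong.* It is not shown to be. The scales of the reduction and the ICC are not given, plausible readings span 88%, and 100 simulations leave wide error.
- *The alpha levels conflict.* One-tailed 0.025 and two-sided 0.05 agree in the direction of benefit.
- *Restricting to baseline-infectious participants erodes the power.* On the literal reading, mixed-model power is 96% with all 20 and 97% in the infectious subset, which is within simulation error.
- *Testing the Section 7.1 percentages against 80% would halve the power.* The protocol plans no such test, and the answer depends on scale. At a true 90% reduction, one-sided Wilcoxon power at 0.025 is about 25% (odds ratio), 43% (logit shift) or 85% (each rate falling by 90%).
- *The 80% hypothesis is meant only for the primaquine arms.* Section 5.4 makes no such restriction.

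**The Section 5.4 model can fail where treatment works best.** If an arm has no infected mosquitoes at day 2, the day effect has no finite maximum-likelihood estimate and a Wald test is unavailable. At a true 99.8% reduction this happens in about 23% to 60% of trials, depending on scale. This stands, and any fix that uses the model must allow for it.

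**Conclusion.** The concern holds for the null hypothesis and the model. The stated 88% is not a property of the analysis in 11.1, and a significant primary result would not show a reduction above 80%, because significance is near certain at a true 50% and likely at a true 30%. The size of the effect rests on the Section 5.4 inputs and on reading the ICC on the latent logit scale. The mismatch in null hypothesis rests on the text alone. The difference in analysis set is secondary. The small number of simulations limits the precision of the power figure and does not show an error in it.

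**What to change.** Align 5.4 with 7.1 and 11.1 in one of two ways.

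**(a) Test what was powered.** Add to 11.1, for each arm, the Section 5.4 mixed-effects logistic estimate of percent reduction. State its scale (risk ratio or odds ratio) and compare its lower 95% confidence limit with 80%. Specify a profile-likelihood, exact or penalised limit for an arm with no infected mosquitoes at day 2. Keep the median percent change as a description.

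**(b) Power what will be tested.** Restate the power in 5.4 for the test, null and baseline-infectious set in 11.1, and call 80% a planning benchmark that is not tested. That power will be close to 100% at a true 90% reduction, so it will say little about why 20 per arm were chosen.

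In both cases, re-run the simulation for the number expected to be infectious at baseline (about 18 of 20 under the stated inputs), with more than 100 replicates and the scales of the reduction and the ICC written down.

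The cost is wording in 5.4 and 11.1, with a matching line in 7.1 under (a), and one simulation run. No participants, visits or assays are added. The stated power may change.
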